## 5. Investigation Plan

### 5.1. Study Design

This is a prospective, post-market interventional, pilot study. Approximately 210 patients will be enrolled in two European centers. At least 15 subjects per month are expected to be enrolled at each participating center. Each subject will be in the study for a maximum period of 72 hours.

Each participating site may involve one or more wards, based on its distribution of surgical high-risk patients. The study is expected to last approximately one year.

## 5.2. Inclusion/Exclusion criteria

All inclusion and exclusion criteria stated in sections 7.3 and 7.4 from CIP, must be met for subjects to be eligible for consent/enrollment inclusion in the study.

The investigator will maintain a log of all subjects enrolled in the clinical investigation. A Subject Identification and Enrollment Log is a document to keep a confidential list of names of all subjects participating in the clinical study.

If a subject is withdrawn from the clinical study, the reason for withdrawal shall be recorded on the Study Exit eCRF and in the subject's medical record.

Possible reasons for withdrawn from the study are:

- Adverse Event;
- Subject withdrew consent;
- Investigator withdrew subject from the study for medical reasons;
- Investigator withdrew subject from the study due to inclusion/exclusion criteria not met.

## 5.3. Overall study design and plan-description

Subjects will be randomly allocated 1:1 to either Capnostream™ 20p or Nellcor Monitoring Systems both in Phase I and in Phase II. The device allocation will be unblinded to both subject and physician.

Continuous monitoring from either Capnostream™ 20p or Nellcor Monitoring Systems will be performed in all subjects for a minimum of 24 hours. The monitoring period will last up to patient's full mobilization or up to a maximum of 72 hours, if the subject is still bed-ridden after two days post-surgery.

During Phase I the alarm feature of the monitoring devices will be silenced, and the screen information blinded. A regular check during the monitoring period should be completed to ensure the EtCO2 filter line and SpO2 sensors are appropriately fitted on the subject.

During Phase II the medical staff will be instructed to respond to alarm feature of the monitoring devices and their screen will be open. A guideline will be created to instruct the nurses in responding to alarms and changes in the monitored parameters on which the nurses will be trained on.

A Flow-chart to schematize the disposition of subjects during the study is presented in Figure 1.

Capnography and pulse oximetry monitoring device data will be collected as well as clinical data related to respiratory compromise. Subjects will be monitored per standard of care.

[figure not shown]
Enrollment at any single site will be limited to 50% (approximately 105 subjects) to ensure poolability of the data across sites and reduce potential bias. Additional methods incorporated to minimize potential bias include the following:

- Systematic identification of potential subjects via screening;

[figure not shown]
- Standard procedures and data collection requirements with a common electronic database for all sites;
- Random allocation to monitoring device.

Foreseeable factors that may compromise the outcome of the study include lack of enrollment or the lack of RC events.

## Figure 1 – Study Flow-chart

One-month minimum period for unblinded device familiarization

Data collection requirements are summarized in Table 1.

**Table 1 - Data Collection Requirements**

Data	Screening Evaluation	Enrollment	Monitoring	Survey (at the study end)
Informed Consent	X			
Inclusion/Exclusion Criteria Evaluation	X			
Medical History		X		
Demographic & Physical Examination		X		
Vital Signs		X	X	
Supplemental Oxygen Use		X	X	
Surgery Information		X		
Monitoring Duration			X	
Medications		X	X	
Number/type of staff interventions (alarm and non-related)			X	
Adverse Events		X	X	
Device Memory Data			X	
Patients' compliance			X	
Product Information			X	
Device Deficiencies			X	
Protocol Deviations	X	X	X	
Clinical staff's satisfaction and workflow impact				X

## 6. Determination of Sample Size

The sample size calculation is based on primary endpoint and it was estimated using data from previous studies with a precision-based calculation. Recent data on post-surgical patient have shown a proportion of patient with the RC markers for the  $\text{SpO}_2 \leq 85\%$  for  $\geq 3$  minutes at 13% and for  $\text{RR} \leq 8$  or  $\geq 22$  bpm for  $\geq 3$  minutes at 1.4% in patients undergoing opioid therapy. Using this information, a minimum proportion of 10% of patients with RC markers with a sample size of 182 subjects will be able to obtain a 95% confidence level with a precision of 5% (ranging from 5% to 10%) and a power of at least 0.80 defined as the probability of achieving the desired precision. Considering a 10% withdrawal or potential dropouts and a potential attrition rate to monitoring compliance of 5% a total of approximately 210 subjects will be enrolled. This cohort will be used prospectively for the blinded and not blinded phase with a ratio 1:2 respectively to minimize not blinded monitored subjects. The blinded phase will enroll

70 subjects randomly allocated 1:1 in the Capnostream 20p and PM1000N arms while the not blinded phase will enroll 140 subjects with same randomized schedule.

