Postoperative hypoxemia it is a strong indicator of patient instability, compromises wound healing and promotes other serious complications, including brain dysfunction, dysrhythmias and myocardial ischemia. Prolonged hypoxic episodes have been reported to be common in hospitalized patients recovering from non-cardiac surgery: up to 37% of patients had at least one episode of oxygen saturation < 90% lasting more than one hour while 3% had saturations <80% for at least 30 minutes.

Postsurgical patients at-risk of developing cardiopulmonary complications could benefit from both preventive interventions and more intensive postsurgical monitoring. Up to 84% of in-hospital cardiopulmonary arrest events are preceded by prolonged periods of physiological and clinical instability. Early intervention of clinically unstable patients by a medical emergency team significantly reduces the incidence of, and mortality from, unexpected cardiac arrest in hospital. A significant decrease in the number of cases of respiratory failure, stroke, severe sepsis, and acute renal failure was also shown after the implementation of a medical emergency team in an Australian study. In 2007, the UK National Institute for Health and Clinical Excellence recommended the use of physiological track and trigger systems to monitor adult patients in acute hospital settings: these systems, also known as Early Warning Scores (EWS), are based on the monitoring of patients' basic physiological observations such as pulse rate, SpO2, blood pressure, respiration rate, temperature and conscious level and are used to identify patients at risk of respiratory failure, cardiac arrest and death. A systematic review has reported that EWS have a strong predictive value for the occurrence of cardiac arrest and death within 48 hours of measurement. EWS has been demonstrated to be effective in predicting clinical deterioration that may lead to a cardiac arrest also in patients in wards that are poorly equipped to detect rapid patient deterioration. National EWS (NEWS), based upon common vital signs such as temperature, respiratory rate, heart rate, systolic blood pressure, nursing assessments of consciousness level of the patient, SpO2 and use of supplemental oxygen is one of the most frequently utilized.

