## 4. Objectives and Endpoints

### 4.1. Objectives

#### 4.1.1. Primary Objective and Endpoint

The primary objective of this study is to quantify the incidence of RC markers in high risk postsurgical patients, using a system comprised of two continuous monitoring devices, connected to a remote monitoring platform.

The occurrence of at least one of the following RC markers will be considered as primary endpoint for patients monitored by Capnostream 20p during both study Phases:

1. SpO2 ≤ 90% for ≥ 3 minutes.
2. RR ≤ 8 or ≥ 22 bpm for ≥ 3 minutes.
3. etCO2 ≤ 15 or ≥ 60 mmHg for ≥ 3 minutes.
4. Apnea episode lasting > 30 seconds.

The occurrence of at least one of the following RC markers will be considered as primary endpoint for patients monitored by PM1000N-RR during both study Phases:

1. SpO2 ≤ 90% for ≥ 3 minutes.
2. RR ≤ 8 or ≥ 22 bpm for ≥ 3 minutes.

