## 12. Statistical Design and Methods

### 12.1 Sample size justification

The sample size calculation is based on primary endpoint and it was estimated using data from previous studies with a precision-based calculation. Recent data on post-surgical patient have shown a proportion of patient with the RC markers for the SpO2 ≤ 85% for ≥ 3 minutes at 13% and for RR ≤ 8 or ≥ 22 bpm

for  $\geq 3$  minutes at 1.4% in patients undergoing opioid therapy. Using this information, a minimum proportion of 10% of patients with RC markers with a sample size of 260 patients will be able to obtain a 95% confidence level with a precision of 5% (ranging from 5% to 10%) and a power of at least 0.80 defined as the probability of achieving the desired precision. Considering a 10% withdrawal or potential dropouts and a potential attrition rate to monitoring compliance of 5% a total of approximately 210 patients will be enrolled. This cohort will be used prospectively for the blinded and not blinded phase with a ratio 1:2 respectively to minimize not blinded monitored patients. The blinded phase will enroll 70 patients randomly allocated 1:1 in the Capnostream 20p and PM1000N-RR arm while the not blinded phase will enroll 140 patients with same randomized schedule.

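### The 10% planning proportion lies below the 13% that the plan itself cites for part of the endpoint, so the claim of 5-point precision with probability 0.80 holds only at about 10% and is not supported at the plan's own figures

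*SAP*

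**What the plan says.** SAP section 6 and Protocol 12.1 describe a precision-based calculation for the primary endpoint. Both start from two published figures: SpO2 "≤ 85% for ≥ 3 minutes at 13" per cent of patients, and 1.4% for the respiratory-rate marker in patients on opioids. From these the SAP moves to "a minimum proportion of 10% of patients with RC markers with a sample size of 182 subjects" and claims a 95% interval with "precision of 5% (ranging from 5% to 10%) and a power of at least 0.80 defined as the probability of achieving the desired precision". Losses of 10% and 5% then lead to about 210 enrolled.

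The primary endpoint is the occurrence of at least one marker: four for Capnostream, two for PM1000N-RR. Its SpO2 component in Protocol 4.1.1 is "≤ 90% for ≥ 3 minutes", not 85%. SAP 4.1 and 7.9.1 also count shorter episodes when an action was taken.

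Protocol 3.1 cites the source of the 13% (Protocol reference 17, SAP reference 3) for a second figure: "up to 37% of patients had at least one episode of oxygen saturation < 90% lasting more than one hour".

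Protocol 12.3 and SAP 7.9.1 report the primary result separately for each arm and phase.

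**The concern.** The sizing input and the endpoint use different SpO2 thresholds, and the planned proportion is lower than the one component quoted to support it. A patient at or below 85% for 3 minutes is also at or below 90% for 3 minutes, and a composite of the at-least-one kind cannot be rarer than any of its parts. On the cited data the composite is therefore at least 13%. A patient below 90% for more than an hour also meets the endpoint, so the same source points to values up to 37%.

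Calling 10% a minimum does not make it cautious. The variance p(1−p) rises with p up to 50%, so the lowest plausible proportion gives the narrowest interval.

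The primary objective is to quantify incidence, and precision is the only design property that the sample size section claims. If the planning proportion is too low, the stated probability of reaching that precision is too high.

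**Working it through.** **Inputs.** Evaluable n = 182, 95% interval, half-width 5 points, probability 0.80, p = 10% (SAP 6); 13% and 1.4% (SAP 6, Protocol 12.1); up to 37% (Protocol 3.1); 70 patients in Phase I and 140 in Phase II, randomised 1:1, so planned cells of 35 and 70.

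**1. The plan's own figure.** For each possible count X out of n, compute the 95% interval and its half-width, then add the Binomial(n, p) probabilities of the counts whose half-width is at most 0.05. At p = 10% the smallest n with probability ≥ 0.80 is 179 (Clopper-Pearson), 161 (Wald or Jeffreys) or 162 (Wilson). The SAP's 182 agrees with the Clopper-Pearson result within 3%. The arithmetic at 10% is sound.

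**2. Same n, other proportions.** At n = 182 the half-width is at most 5 points if X ≤ 22 (Clopper-Pearson), X ≤ 24 (Wald, Wilson) or X ≤ 25 (Jeffreys), for counts below one half. The probability is therefore P(X ≤ cut-off):

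| True proportion | Clopper-Pearson | Wald / Wilson | Jeffreys |
|---|---|---|---|
| 10% | 0.855 | 0.935 | 0.959 |
| 13% | 0.409 | 0.584 | 0.666 |
| 14.4% (13 + 1.4, no overlap) | 0.220 | 0.368 | 0.450 |
| 37% | 0.000 | 0.000 | 0.000 |

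The probability drops below 0.80 once p exceeds about 10.5% (Clopper-Pearson), 11.5% (Wald, Wilson) or 12.0% (Jeffreys). All three lie below 13%.

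**3. Typical half-width at n = 182.** At 13% (24 events): 4.9 points (Wald, Wilson, Jeffreys) or 5.2 (Clopper-Pearson). At 37% (67 events): 7.0 (Wald) or 7.2 (Clopper-Pearson).

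**4. Even with no losses.** With all 210 evaluable, the probability at 13% is 0.75 (Clopper-Pearson) or 0.93 (Wald); at 37% it is still 0.

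**5. Wald half-widths, 1.96 × √(p(1−p)/n), in percentage points.**

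| n | 10% | 13% | 37% |
|---|---|---|---|
| 180 (pooled) | 4.4 | 4.9 | 7.1 |
| 70 (Phase II, one arm) | 7.0 | 7.9 | 11.3 |
| 35 (Phase I, one arm) | 9.9 | 11.1 | 16.0 |

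For example, n = 35 and p = 10%: 1.96 × √(0.09/35) = 0.099. The pooled worst case, at p = 50%, is 1.96 × √(0.25/180) = 0.073. The cell figures are before attrition.

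**The case against.** The plan ties its claim to 10%, and at 10% it is true. This is therefore an unjustified assumption and not a miscalculation. At 13% the typical Wald half-width is still 4.9 points, so the shortfall there is in the stated probability more than in the width. The 37% is an upper figure from another study, so a half-width of about 7 points belongs to that scenario alone. All of this stands.

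The bound of 13% also applies within the cited data, not automatically to this trial. The other site's physician adjudicates potential episodes using device and clinical data (SAP 7.9.1), and two-thirds of patients are in Phase II, where staff respond to alarms. Either could lower the rate. This stands as a limit on what can be predicted, but neither document uses it to justify 10%.

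Three stronger readings are tempting, and the documents do not support them:

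- *Readers of the results will be misled about precision.* The results carry their own observed 95% confidence intervals, and the planning half-width enters no analysis.
- *The stated losses leave too few patients even at 10%.* 210 × 0.85 = 178.5 and 210 × 0.90 × 0.95 = 179.6. The Clopper-Pearson probability at 10% is 0.756 at n = 178 but 0.817 at 179 and 0.810 at 180, so the apparent failure is a rounding effect. The plan also says approximately 210.
- *The bracketed 5% to 10% is a wrong interval.* It does not match 10% ± 5 points, which is 5% to 15%. It could instead mean acceptable half-widths of 5 to 10 points, and then 7 would fit, but that sits badly with a stated precision of 5%. It is ambiguous and not shown to be wrong.

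**Conclusion.** The concern holds as a fault in the planning input. The plan cites 13% for a stricter version of one component and then, without explanation, sizes the composite on 10%. Its claim of 5-point precision with probability at least 0.80 at n = 182 is correct at 10% and fails above about 10.5% to 12%. At the plan's own 13% the probability is 0.41 to 0.67 across the four interval methods checked; at 37% it is 0.

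This rests on 182 evaluable patients pooled over arms and phases, and on the trial's rate resembling that of the cited source. The SAP does not name the interval method for the proportion, hence the ranges. The size of any real shortfall depends on a rate that is not yet known. The pooled figures also do not describe the cells that will be reported: with 35 or 70 patients the half-width exceeds 5 points even at 10%.

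Should be fixed. In a descriptive pilot it changes no analysis, but the stated probability cannot stand next to the inputs given for it.

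**What to change.** Keep 210 patients and reword SAP 6 and Protocol 12.1:

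- Base the statement on SpO2 ≤ 90% and the composite endpoint. If 10% is kept, give the reason for going below 13%.
- Tie the 0.80 probability explicitly to a true proportion of 10% and name the interval method, or delete it.
- Say what the bracketed range of 5% to 10% means, or delete it.
- Give Wald half-widths over a range. For the pooled cohort of about 180: 4.4 points at 10%, 4.9 at 13%, 7.0 to 7.1 at 37%, worst case 7.3. For the reported cells before attrition, at 10%, 13% and 37%: 9.9, 11.1 and 16.0 points with n = 35; 7.0, 7.9 and 11.3 with n = 70.

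Protocol 12.1 still gives 260 where the SAP gives 182. That is a separate discrepancy, but it sits in the same sentence and can be corrected in the same edit.

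The cost is wording in two sections and a less favourable precision statement. No patients, procedures or analyses are added.

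### The sample-size sections print a precision of 5 points around 10% as a range of 5% to 10%; the matching range is about 5% to 15%

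*SAP*

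**What the plan says.** SAP section 6 describes the sample size by saying that "it was estimated using data from previous studies with a precision-based calculation". The planning statement is "a minimum proportion of 10% of patients with RC markers with a sample size of 182 subjects", and the target is a "95% confidence level with a precision of 5% (ranging from 5% to 10%) and a power of at least 0.80". Power here does not refer to a hypothesis test; it is "defined as the probability of achieving the desired precision". After allowances of 10% for dropout and 5% for monitoring compliance, "a total of approximately 210 subjects will be enrolled".

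Protocol section 12.1 carries the same sentence with the same parenthesis and the same enrolment, but gives 260 in place of 182.

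Neither document explains the range in the parenthesis, and neither prints 5% to 15% anywhere. Protocol 12.3 reports the proportion of patients with at least one RC marker, with 95% confidence intervals, separately for each arm and phase; SAP 7.9.1 does the same for event rates.

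**The concern.** The primary objective is to quantify an incidence, so the sample-size section has one job: to tell the reader how tightly that incidence will be estimated. It gives a planning value of 10%, a precision of 5% and a range of 5% to 10%. The first two imply a range that the third does not match. An interval that ends at the value it is meant to surround cannot be a two-sided interval around that value.

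What is at stake is the accuracy of the stated precision. Someone who takes the parenthesis as the expected confidence limits would plan on an upper limit of 10%, where the design gives about 15%.

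**Working it through.** **Inputs** (SAP 6 unless noted): planned proportion p = 0.10; 95% confidence; precision 5 points; probability of reaching it at least 0.80; 182 evaluable; about 210 enrolled. Protocol 12.1 has 260 in place of 182. Neither document names an interval method for the proportion, so the exact, Wald and Wilson methods were all tried.

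**1. Reproduce the plan's 182.** Read precision as the half-width h of the 95% interval. Find the smallest n with P(h ≤ 0.05 | n, p = 0.10) ≥ 0.80, summing binomial probabilities over the event counts that satisfy the condition.

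- Exact (Clopper-Pearson): n = 179. At n = 182 the half-width is at most 5 points when there are 22 events or fewer, and P(X ≤ 22 | 182, 0.10) = 0.855.
- Wald: n = 161 (at or above 0.80 for every n from 165). Wilson: n = 162 (likewise from 165). At n = 182 both give 0.935.
- Wald with no probability requirement: n = 1.96² × 0.10 × 0.90 / 0.05² = 138.3, so 139.

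The exact calculation lands within 3 patients of 182. The enrolment also follows: 182 × 1.15 = 209.3, and 182 / 0.85 = 214.1; both are close to 210.

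**2. The range that goes with that precision.** 10% − 5 = 5% and 10% + 5 = 15%. The intervals at an observed value near 10% are:

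| Evaluable n | Events | Exact 95% interval | Wilson | Wald |
|---|---|---|---|---|
| 182 | 18 | 6.0% to 15.2% | 6.3% to 15.1% | 5.6% to 14.2% |
| 210 | 21 | 6.3% to 14.9% | 6.6% to 14.8% | 5.9% to 14.1% |
| 260 | 26 | 6.6% to 14.3% | 6.9% to 14.2% | 6.4% to 13.6% |

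**3. Could 5% to 10% be the limits of any interval the study might report?** No event count out of 182, 210 or 260 gives a 95% interval lying inside 5% to 10% by any of the three methods. For example, with exact limits at n = 182, the lower limit first reaches 5% at 16 events, where the upper limit is 13.9%; the upper limit is at or below 10% only with 10 events or fewer.

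**4. What the 5 points cover.** The plain Wald half-width at 10% is 1.96 × √(0.09 / n):

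| n | What it is in the plan | Half-width (points) |
|---|---|---|
| 182 | pooled, evaluable | 4.4 |
| 140 | Phase II, enrolled | 5.0 |
| 70 | Phase I, or one Phase II arm, enrolled | 7.0 |
| 35 | one Phase I arm, enrolled | 9.9 |

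The 5-point precision belongs to the pooled cohort. The arm-by-phase estimates that will be reported have half-widths of about 7 to 10 points, before any losses.

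**The case against.** The strongest reply is that the parenthesis may not be meant as confidence limits. Three other readings deserve a fair hearing.

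- **A range of half-widths, 5 to 10 points.** Grammatically the parenthesis qualifies the word precision, and the Wald half-widths at the planned group sizes do run from 5.0 points (n = 140) to 9.9 points (n = 35). This fits well. However, neither document says so, and the 0.80 is attached to a single desired precision of 5%.
- **The span from the lower limit to the estimate.** 10 − 5 = 5, which suits a sentence that calls 10% a minimum. It is possible, but it leaves out the upper limit, and the text does not say that this is what is shown.
- **A one-sample comparison of 5% with 10%.** n = ((1.96 × √0.0475 + 0.842 × √0.09) / 0.05)² ≈ 185 at 80% power, and about 264 at 90%; these are close to 182 and 260. But the documents describe a precision calculation, state no null value and define power as the chance of reaching the precision.

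It therefore cannot be claimed that the printed range fits no reading at all. What stands is that none of these readings is stated, so the sentence needs correcting or explaining in any case.

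It is also fair to reply that the correct interval can be worked out from the 10% and the 5% in the same sentence. That limits the harm; it does not make the printed range right.

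A reader might go further and infer that the study is too small, because an interval only 5 points wide (half-width 2.5) with probability 0.80 would need roughly 600 to 640 patients at 10%. The documents do not support this: they claim a precision of 5 points, never 2.5, and 182 delivers it. Nor does the plan set out to rule out 15%, since 10% is described as a minimum.

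**Conclusion.** The point holds as an error in the stated precision, not in the design. In both documents the range of 5% to 10% does not match a 5-point precision around 10%; the matching range is 5% to 15%. Taken as confidence limits, the printed upper end is about 5 points too low.

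The 182 is sound for the stated target: the probability of a half-width of at most 5 points is 0.855 with exact intervals and higher with Wald or Wilson. Enrolment of 210, the endpoints and the analyses are unaffected.

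This rests on two assumptions: that precision means the half-width of a two-sided 95% interval, and that the planned proportion is 10%. The close reproduction of 182 supports both. If the sponsor meant one of the other readings, the range is unexplained and not wrong, and the sentence still needs rewording.

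**What to change.** In SAP 6 and Protocol 12.1, replace the parenthesis with: *half-width of at most 5 percentage points, i.e. about 5% to 15% around 10%*. Add a sentence saying that this precision applies to the pooled cohort and not to the separate arm-by-phase estimates. If a different meaning was intended, state that meaning explicitly.

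In the SAP, the exact interval at 18 of 182 (6.0% to 15.2%) may be added as an illustration, labelled as Clopper-Pearson because the plan names no method.

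In Protocol 12.1, reconcile the 260 with the SAP's 182 in the same edit, before quoting any interval that depends on n. The 260 exceeds the 210 to be enrolled, and 260 / 0.85 = 306 does not lead to 210. That is a separate inconsistency, but it sits in the same sentence, and inserting an interval for 182 beside it would leave two sample sizes side by side.

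The cost is one reworded sentence in each document. The stated precision will look less favourable. Enrolment stays at 210.
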